7.2.2 Treatment Compliance and Modifications

Study treatment will be administered to the patient at the study site by trained study staff. Patients compliance with the prescribed regimen will be assured as all administrations will be performed by site staff under the supervision of the study investigator or his/her designee. Therefore, no analysis of compliance is planned. However, dose interruptions and reductions may occur (see Section 8.6).

8 Safety Analysis

Safety analysis will be conducted on the SAF for the Phase I dose escalation and separately for the Phase II expansion cohorts. Combined outputs for safety may be produced based on the Safety RP2D Analysis Set.

8.1 Dose-Limiting Toxicity

The incidence of DLTs is the primary endpoint in Phase I. The specific type and grades of AEs classified as a DLT can be found in the protocol in Section 6.12. The DLT observation period for the Phase I dose escalation cohorts is explained in Section 3.4.

The number and percentage of patients with at least one DLT will be presented by dose group (as defined in Section 4.2.1).

A listing of key information for DLTs will be presented including patient identification number, Preferred Term (PT) of corresponding AE and CTCAE grade. DLT information will be reported and summarized for Phase II whenever appropriate

8.2 Adverse Events

All AEs regardless of study drug relationship will either be collected from the signing of consent up to the end of the 30 day follow-up based on current protocol versions 3.0 and 4.0 or 90 day follow up based on the previous protocol versions. Those AEs with onset 31-90 days after the last dose will be flagged in the separate adverse events listing.

- 1) Treatment-emergent adverse events (TEAEs) are defined as any adverse event after the first dose of study drug within 30 days of the last dose of study drug or prior to subsequent anti-cancer therapy, whichever is sooner. For adverse events on C1D1, the event onset time relative to the first dose time will be considered (if relative or actual times are available), otherwise AE starting on C1D1 will be assumed treatment-emergent.

The AE summary tables include only AEs that are new or worsened during the on-treatment period (TEAEs). However, all safety data (including those from the pre- and post-treatment periods) will be listed and those collected during the pre-treatment and post-treatment period are to be flagged.

The incidence of TEAEs will be summarized by system organ class (SOC) and/or PT, severity (based on NCI CTCAE v.4.03 grades), and relation to study treatment by treatment group (as defined in Section 4.2.1). Serious TEAEs resulting in death and non-fatal serious TEAEs will be listed by patient and tabulated by treatment group. There will be a separate listing for TEAE leading to treatment discontinuation.

AEs will be coded by MedDRA version 20.0.

For the purpose of inclusion in TEAE tables, incomplete AE onset and end dates will be imputed as follows:

- Missing onset dates (where UK and UKN indicate unknown or missing day and month respectively):
 - UK-MMM-YYYY: If the month and year are different from the month and year of the first dose of study drug, assume 01-MMM-YYYY. If the month and year are the same as the first dose of study drug month and year, and the end date (after any imputation) is on or after the first dose of study drug, then assume the date of the first dose of study drug. If the month and year are the same as the first dose of study drug month, and year and the end date (after any imputation) is prior to the first dose of study drug, then assume the end date for the onset date.
- Missing end dates are generally not imputed. However, in the cases of partial missing end dates, the following rules will be applied (where UK and UKN indicate unknown or missing day and month respectively):
 - UK-MMM-YYYY: Assume the last day of the month.
 - DD-UKN-YYYY/UK-UKN-YYYY: Assume 31-DEC-YYYY.

8.2.1 Incidence of Adverse Events

An overall summary of the number and percentage of patients with at least one TEAE in different categories (described here and below) will be provided by treatment group (as defined in Section 4.2.1). Treatment-emergent AEs will also be presented by SOC and PT. At each level of patient summarization, a patient is counted once if the patient reported one or more events. Percentages will be calculated out of the number of patients in the SAF. The table is sorted alphabetically for SOC and by descending frequency overall for PT.

Additionally, a summary of TEAEs will be presented by PT alone sorted in descending order of frequency overall. In addition, AEs of special interest including CRS (i.e. cytokine release syndrome [CRS]) symptoms will be presented in separate tables as needed.

All AEs will be presented in a listing.

8.2.2 Relationship of Adverse Events to Study Drug

A summary of TEAEs related to study drug will be presented in a table by incidence of occurrence. The investigator will provide an assessment of the relationship of the event to the study drug. The possible relationships are “related”, “possibly related” and “unrelated”. All “related” and “possibly related” AEs and SAEs will be defined as related to study drug.

In the TEAE relationship table, if a patient reports multiple occurrences of the same TEAE, the highest grade of the related or possibly related will be presented (e.g. if a patient experiences for example Grade 3 dyspnea that is ‘potentially related’ and Grade 1 dyspnea that is ‘related’, it would give that patient a maximum severity of Grade 3 rather than Grade 1 in the TEAE relationship table). Treatment-emergent AEs that are missing a relationship will be presented in the summary table as “related” but will be presented in the data listing with a missing relationship. Percentages will be calculated based on the number of patients in the SAF.

The TEAE related to study drug data will be presented by SOC, PT and maximum severity (see below), and PT alone in a manner similar to that described in Section 8.2.1.

8.2.3 Severity of Adverse Event

A summary of TEAEs by severity will be presented in a table. The severity that will be presented represents the most extreme severity captured on the eCRF page. The possible severities are measured on the CTCAE scale which goes from 1 to 5 where 1="mild", 2="moderate", 3="severe", 4="life-threatening" and 5="fatal". In the TEAE severity tables, if a patient reported multiple occurrences of the same TEAE, only the most severe will be presented. Treatment-emergent AEs that are missing severity will be presented in tables and listings as "missing". Percentages will be calculated out of the number of patients in the SAF.

The TEAE data will be presented by SOC, PT and maximum severity in a manner similar to that described in Section 8.2.1. Extra columns will be added to show TEAEs having CTCAE grade 3-4 and 5 separately. Additionally, the grade 3 and 4 TEAEs and related TEAEs will be presented by PT alone.

8.2.4 Serious Adverse Events

Treatment-emergent serious adverse events (SAEs) will be presented in a table. Treatment-emergent SAEs related to study drug will be presented in a table. A treatment-related treatment-emergent SAE is a treatment-emergent SAE with any relation to study drug other than "unrelated". Treatment-emergent SAEs that are missing a relationship will be presented in the table as "related" but will be presented in the data listing with a missing relationship. At each level of patient summarization, a patient is counted once if the patient reported one or more events. Percentages will be calculated out of the number of patients in the SAF.

The treatment-emergent SAE data will be categorized and presented by SOC and PT, and PT alone in a manner similar to that described in Section 8.2.1.

8.2.5 Adverse Events Leading to Treatment Discontinuation, Dose Interruption and Dose Reduction

A summary of TEAEs with a study drug action taken of "drug discontinued", "dose interrupted" and "dose reduced" will be presented in separate tables. At each level of patient summarization, a patient is counted once if the patient reported one or more events. Percentages will be calculated out of the number of patients in the SAF.

The tables will be presented by PT in descending order of frequency from the PT with the highest total incidence (that is, summed across all treatment groups, as defined in Section 4.2.1) to the PT with the lowest total incidence.

8.2.6 Deaths

TEAEs with an outcome of "fatal" will be presented in the overall summary table. A patient is counted once if the patient reported one or more events. Percentages will be calculated out of the number of patients in the SAF.

All patients who have a TEAE with an outcome of "fatal" will be presented in a listing. A listing of all deaths recorded during the study will also be produced. This listing will include the cause of

death and the period that the event occurred (i.e. the treatment period plus 30 days from last dose administered or the follow-up period).

8.3 Clinical Laboratory Evaluations

Laboratory parameters assessed for safety purposes will be evaluated locally. Refer to **Table 4** for a summary of the parameters to be evaluated. Local laboratories must provide normal ranges for the parameters being analyzed and accreditation documentation for all local laboratories that perform protocol-required assessment.

Approved

Table 4 - Clinical Laboratory Parameters Collection

Test Category	Test Name
Hematology	Hemoglobin, platelets, white blood cells, lymphocytes, and neutrophils
Chemistry	Albumin, alkaline phosphatase, alanine transaminase, aspartate transaminase, bicarbonate, calcium, chloride, creatinine, glucose magnesium, inorganic phosphate, potassium, sodium, total bilirubin (also measure direct and/or indirect bilirubin if total bilirubin is $> 1.5 \times \text{ULN}$), blood urea nitrogen or urea, amylase, and lipase
Coagulation	Prothrombin time or international normalized ratio and activated partial thromboplastin time
Urinalysis	Bilirubin, blood, glucose, ketones, pH, protein, specific gravity, and white blood cells (in the event of macroscopic findings, microscopy may be performed at the Investigator's discretion)
Thyroid	Free T4 and thyroid stimulating hormone (also measure free T3 if TSH is suppressed but free T4 is normal)
Pregnancy / menopausal status	hCG (women of childbearing potential) FSH (if required to confirm non-childbearing potential)

hCG = human chorionic gonadotropin; FSH = follicle-stimulating hormone; T3 = triiodo thyroxine; T4 = thyroxine; TSH = thyroid stimulating hormone.

Pregnancy tests will be performed for all women of childbearing potential. Any pregnancy must be reported as described in Section 8.5.6 of the protocol V4.0, and the patient should be withdrawn from treatment. For post-menopausal patients, FSH at screening must be within the laboratory's post-menopausal reference range.

In addition to laboratory parameters obtained by local laboratories, the following parameters will be derived (age and weight will be the values at Cycle 1 Day 1):

- For patients with Albumin < 40 g/L, Corrected calcium (mmol/L) = Total calcium (mmol/L) + $([40 - \text{Albumin (g/L)}] \times 0.02)$. Otherwise, Corrected calcium (mmol/L) = Total calcium (mmol/L)
- Creatinine clearance (mL/min)
 - For males = $[140 - \text{age}(\text{years})] \times \text{weight}(\text{kg}) / [72 \times \text{serum creatinine (mg/dL)}]$
 - For females = $0.85 \times [140 - \text{age}(\text{years})] \times \text{weight}(\text{kg}) / [72 \times \text{serum creatinine (mg/dL)}]$
- If only % lymphocytes reported then:
Absolute lymphocytes = white blood cell count \times % lymphocytes
- If only % neutrophils reported then:
Absolute neutrophils = white blood cell count \times % neutrophils

On dosing days laboratory safety samples will be collected prior to the IMCnyeso infusion. More frequent evaluations may be performed, at the investigator's discretion, if medically indicated; results should be recorded as unscheduled laboratory assessments in the eCRF.

Laboratory parameters obtained by local laboratories and derived parameters will be summarized. Any result below the limit of quantification (BLQ) where BLQ for a parameter is clinically relevant (Hemoglobin, WBC, Lymphocyte count, Neutrophil count, Platelet count, Albumin, Bicarbonate, Calcium, Chloride, Magnesium, Phosphorus, Potassium, Sodium, Glucose, TSH, Free T4, Free T3) will be included in the calculation of standard statistics listed in Section 4 with the result set as 0.

Some results might be expressed as a range rather than a single value (e.g. '<x'). For such results, the value to be considered for summaries is the upper limit of the range if 'x' is greater than the BLQ (e.g. for '<x' results, the value will be 'x'). If 'x' is the BLQ, the result cannot be included in the statistics calculations as explained above.

For laboratory tests covered by the NCI CTCAE version 4.03, the study team will grade laboratory data accordingly and grading programming will be performed at SDTM database. For laboratory tests covered by NCI CTCAE, a grade of 0 will be assigned for all non-missing values not graded as 1 or higher. For laboratory tests where grades are not defined by CTCAE, results will be graded by the low/normal/high classifications based on laboratory normal ranges.

For NCI CTCAE tests, the worst on-treatment result is the maximum grade recorded after baseline. For non-NCI CTCAE tests, the worst on-treatment result will be:

1. "Low", if any result recorded after baseline is lower than the normal range and no post-baseline result is higher.
2. "High", if any result recorded after baseline is higher than the normal range and no post-baseline result is higher.
3. "Both", If both low and high are clinically meaningful, report worst low and worst high separately.

Summaries will be generated separately for hematology and biochemistry. These will include:

- Absolute values and change from baseline summaries, a graph of the results will be plotted.
- Shift tables of laboratory data using CTCAE grades to compare baseline to the worst on-treatment value, a graph of the results will be plotted.
- Listing of all relevant laboratory data with values flagged to show the corresponding CTCAE grades and the classifications relative to the laboratory normal ranges.

Shift tables of baseline to worst on-treatment laboratory grade (low/normal/high) will be presented for the following parameters with their relative worsening direction:

- Low: Hemoglobin, Albumin, Platelets, Neutrophils, and Phosphate.
- High: ALP, ALT, APTT, AST, Total bilirubin, Creatinine, Amylase, Lipase, and INR.
- Both: WBC Count, Lymphocytes, Calcium, Magnesium, Sodium, Potassium, Corrected calcium, and Glucose.

Central laboratory cytokine data (Interferon Gamma, Interleukin 6, Interleukin 8, Tumor Necrosis Factor alpha, Interleukin 10, Interleukin 2) will be summarized and statistics produced as per Section 4. A graph of the results will be plotted by all timepoints. It will also be listed.

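### SAP 8.3: the rule for a High worst on-treatment value in non-CTCAE laboratory tests repeats the Low rule's exclusion and, read consistently, can never be met

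*SAP*

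**What the plan says.** SAP 8.3 handles two kinds of laboratory test. For graded tests, "For NCI CTCAE tests, the worst on-treatment result is the maximum grade recorded after baseline". The other rule opens with "For non-NCI CTCAE tests, the worst on-treatment result will be" and has three numbered items:

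- Item 1, Low: "if any result recorded after baseline is lower than the normal range and no post-baseline result is higher".
- Item 2, High: "if any result recorded after baseline is higher than the normal range and no post-baseline result is higher".
- Item 3, Both: where the two directions both matter clinically, the worst low and the worst high are shown separately.

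Further on, the same section promises shift tables from baseline to worst low/normal/high class and lists a worsening direction for each parameter. Five parameters are listed as Low, nine as High ("High: ALP, ALT, APTT, AST, Total bilirubin, Creatinine, Amylase, Lipase, and INR") and eight as Both, which makes 22. The planned outputs in SAP 14.2 include low/normal/high shift tables for hematology (14.3.4.3.2.1) and biochemistry (14.3.4.7.2.1), next to separate CTCAE-grade shift tables (14.3.4.3.1.1 and 14.3.4.7.1.1).

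**The concern.** Items 1 and 2 are meant to mirror each other: a value on one side of the range and none on the other. Item 1 does this. Item 2 ends with the same word as item 1, so its exclusion refers to the direction it is meant to detect.

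A programmer who follows the text therefore has to choose between a condition that cannot be satisfied and a clause that does nothing. At stake is whether high values appear in the worst-value classification of the tests under this rule. Because SAP 8.3 gives no other definition of a worst low/normal/high value, the same choice may carry into the two low/normal/high shift tables. Laboratory changes are listed among the Phase I primary endpoints and the Phase II secondary endpoints in SAP 3.2, so the display should rest on a rule that can be executed.

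**Working it through.** The plan states no figure on this point, so there is none to reproduce. The check is one of logic.

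**Inputs.** Items 1 and 2 of SAP 8.3 as quoted. Each post-baseline result is low, normal, high or very high. All sequences of 1 to 4 results were enumerated: 4 + 16 + 64 + 256 = 340. They divide as follows:

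- All normal: 4.
- Low but no high: sequences of low and normal only number 2 + 4 + 8 + 16 = 30; less the 4 all-normal, 26.
- High but no low: sequences of normal, high and very high number 3 + 9 + 27 + 81 = 120; less the 4 all-normal, 116.
- Both low and high: 340 − 4 − 26 − 116 = 194.

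Sequences containing a high value number 116 + 194 = 310. These are logical possibilities, not expected patient frequencies.

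**Two readings of the closing word.** Reading A: higher than the normal range. Reading B: higher than the result in question.

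- Item 2 under A requires a value above the range and no value above the range. This is impossible.
- Item 2 under B requires a value above the range that no other result exceeds. The patient's own maximum always meets this, so the clause removes nobody.
- Item 1 under A requires a value below the range and none above it. This works.
- Item 1 under B requires a low value that no other result exceeds. A single normal result defeats it.

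| Item 1 / item 2 | Low without high (26) | High without low (116) | Mixed (194) |
|---|---|---|---|
| A / A | 26 Low | 0 High | none labelled |
| A / B | 26 Low | 116 High | 194 High |
| B / B | 4 Low, 22 unlabelled | 116 High | 194 High |
| A / item 2 mirrored to lower than the range | 26 Low | 116 High | none labelled by items 1 and 2 |

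Reading A is the only one under which item 1 classifies all 26 low-without-high sequences. Carried into item 2, it gives High in 0 of 310. Mirroring item 2 restores 116 of 116 and leaves the mixed sequences to the direction rule.

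**Is it corrected elsewhere?** Protocol 9.6.2.2 calls for low/normal/high classification but gives no worst-value rule for it. SAP 12, on changes in the planned analysis, does not mention it. Item 3 does not repair item 2: it depends on whether both directions matter for the test, and under reading A it gives no label to a patient on a one-directional test whose abnormal values are all high.

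**The case against.** The best reply is that this is a copying slip with little practical consequence. The direction list shows what was meant, and a programmer would probably build the tables from it. Observed values, changes from baseline and listings flagged against the normal range would still show every high result. All of this stands and limits the severity. It does not make item 2 coherent.

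Scope is also narrow. The three items are headed for non-CTCAE tests only. Protocol Table 6-3 itself refers to grades for neutropenia, thrombocytopenia, anemia, lymphopenia, ALT/AST, bilirubin, amylase/lipase and electrolytes, so many of the 22 listed parameters have a CTCAE grade and their own grade-based shift table. The documents do not say which listed parameters fall under items 1 to 3. Their use in the low/normal/high shift tables is an inference from the absence of any other definition.

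A reader might go further and infer that, under reading B, every patient with both low and high values is misclassified and belongs in a patient-level Both category. The documents do not support that. Item 3 treats Both as a property of the test, and the direction list assigns it by parameter. For a parameter listed as High, showing such a patient as High agrees with the list. For the eight two-directional parameters, worst low and worst high are reported separately, so the low is not hidden. SAP 8.4 treats vital signs the same way. Redefining Both by patient would conflict with the list: an ALT patient with one low and one high value would become Both, although ALT is listed as High only.

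**Conclusion.** Item 2 is wrong as written, and nothing else in the SAP or protocol corrects it. On the reading that makes item 1 work, it never assigns High. On the other reading, its exclusion clause is empty. The finding concerns non-CTCAE tests and, if the same definition is used there, tables 14.3.4.3.2.1 and 14.3.4.7.2.1.

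The mention of laboratory changes among the Phase I primary endpoints might suggest that a primary result is at risk. It is not: the Phase I primary variable is DLT occurrence (Protocol 9.5.1), and SAP 4 states that no formal hypotheses are tested. CTCAE maximum-grade tables, DLT assessment, dose decisions and the response rate do not use this rule. This is a minor specification error in a descriptive safety display, worth correcting because the text cannot be executed as it stands. The number of patients affected cannot be estimated from the documents.

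**What to change.** In SAP 8.3:

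1. Change the closing clause of item 2 so that High requires at least one post-baseline value above the normal range and none below it.
2. State in item 1 that higher means above the normal range.
3. Keep Both as the parameter-level rule of item 3 and the direction list, with worst low and worst high reported separately for the eight two-directional parameters.
4. Add that for one-directional parameters the worst value is taken in the listed direction, so that patients with values on both sides of the range are not left unlabelled.
5. Say whether items 1 to 3 also govern the low/normal/high shift tables.

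The cost is a few words of SAP text before programming is locked. No data collection, sample size or timeline is affected.

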8.4 Vital Signs

Vital signs (body temperature, pulse, respiratory rate, and blood pressure) will be performed as scheduled (details see Table 7-2 of the protocol V4.0).

Vital signs pre-dose values and worst absolute values and changes from pre-dose as well as time from start of infusion to worst will be summarized for each dose. See Section 9 of the protocol V4.0 for definition of observation periods.

The relevant vital sign values at each visit will be classified into the categories of low, normal, and high based on the following reference ranges.

- Systolic blood pressure, low is <75 mm Hg or decrease of ≥ 30 mm Hg that results in ≤ 90 mm Hg. High is ≥ 160 mm Hg. (CTCAE V4.03, Grade 1: Prehypertension (systolic BP 120 - 139 mm Hg), Grade 2: Stage 1 hypertension (systolic BP 140 - 159 mm Hg), Grade 3: Stage 2 hypertension (systolic BP ≥ 160 mm Hg))
- Diastolic blood pressure, low is <40 mm Hg or decrease of ≥ 20 mm Hg that results in ≤ 50 mm Hg. High is ≥ 100 mm Hg. (CTCAE V4.03, Grade 1: Prehypertension (diastolic BP 80 - 89 mm Hg), Grade 2: Stage 1 hypertension (diastolic BP 90 - 99 mm Hg), Grade 3: Stage 2 hypertension (diastolic BP ≥ 100 mm Hg))
- Pulse, low is <60 bpm. High is >100 bpm.
- Temperature, low is ≤ 32 °C. High is ≥ 38 °C for any fever and >40 °C for CTCAE grade 3 fever. (CTCAE V4.03, 1. Fever- Grade 1: 38.0 - 39.0 degrees C, Grade 2: >39.0 - 40.0 degrees C, Grade 3: >40.0 degrees C for ≤ 24 hours, Grade 4: >40.0 degrees C for > 24 hours; 2. Hypothermia- Grade 2: 35 - >32 degrees C; Grade 3: 32 - >28 degrees C; Grade 4: ≤ 28 degrees C)
- Weight gain: grade 1 = 5 - <10% from baseline, grade 2 = 10 - <20% from baseline, grade 3 = $\geq 20\%$ from baseline.
- Weight loss: grade 1 = 5 - <10% from baseline, grade 2 = 10 - <20% from baseline, grade 3 = $\geq 20\%$ from baseline.
- Oxygen saturation, low is < 94% and <88% is Grade 3.

For those parameters where the values might go in multiple directions (low/high), the results will be presented for worst low post-baseline and worst high post-baseline results separately. Figures for vitals during cycle 1, with all timepoints from pre-dose through ~24 hours post-dose will be plotted.

